## 2.8 Recruitment

The Chief Investigator will agree suitable times to visit participating wards with the relevant ward managers and/or matrons. Ward managers will circulate study information to their nurses in advance of this time. At agreed times, the Chief Investigator will visit wards and confirm with the nurse in charge that staffing levels and patient care requirements mean it is still safe for data collection to proceed. He will then invite staff to participate in a data collection session and agree a safe time (that day) for this to happen.

# 3 METHODS: ASSIGNMENT OF INTERVENTIONS

## 3.1 Sequence generation

The allocation sequence will be generated using an online blocked randomisation list generator (www.sealedenvelope.com/simple-randomiser/v1/lists). A block size of 10 will be employed. Allocation will be stratified by research site and nursing experience, to ensure equal representation of nurses employed by different hospitals and with different levels of experience in each group.

Nursing experience will be measured by the total number of years each participant has been accredited for the administration of intravenous medicines, with two strata: <5 years and ≥5 years. A cut off of five years of experience preparing and administering intravenous medicines was chosen because evidence suggests that the number of errors with which a nurse is involved decreases over the first four to six years of their nursing experience. In particular, one study found that the risk of intravenous medicine administration errors decreased with each year of a nurse's experience up to six years.

The allocation sequence will link each participant's unique randomisation code to their allocation groups: A or B.

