## 1.5 Study design

This study will be a single-blind, randomised parallel group *in situ* simulation experiment with a 1:1 allocation ratio. It is designed to determine whether the user tested guide is superior to the original guide.

*In situ* simulation involves a simulated episode of patient care integrated into a clinical environment with participants who are on duty health professionals. It is therefore useful in patient safety research if it is not feasible to test interventions during routine patient care, while still allowing participants to experience the time pressures and distractions present in the clinical environment.

During the simulation, each participant will prepare an infusion of an intravenous medicine ("bathicillin") in response to a simulated inpatient medication order for an adult. They will then administer this dose to a training manikin arm. During this process, they will be observed by a researcher, who will note any preparation or administration errors.

One group will use the "original" IMG monograph to guide this process and the other group will use the "user tested" IMG monograph. The groups will be treated identically in all other respects. As cross-over design will not be utilised, as this would create a serious order effect.

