A power calculation accounting for clustering (using STATA) indicates that a sample size of 43 participants per group per cluster will give an 80% probability of detecting the above reduction in the moderate-severe error rate at the 5% significance level. This assumes an intraclass correlation coefficient of 0.01, which is low, but justifiable given the similarities in nurse training and procedures discussed above. As it is anticipated that four hospitals is the most likely number of study sites, this equates to a sample size of 172 participants per group.

Given that likely recruitment rates are not accurately known, this study will therefore achieve a minimum sample size of 121 participants per group, but may increase this up to 172 participants per group if recruitment is sufficiently quick. This larger sample size would provide greater power to analyse the effect of hospital site (and other variables, see Section 4.3) on the outcomes.

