## 3.3 Implementation

The allocation sequence will be generated and uploaded to the online randomisation service by a person independent from the research team. The Chief Investigator will enrol participants and randomly assign them to one of the study groups.

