## Debrief interview

Following completion of the observational data collection, each participant who was observed to make an IMG-related error will be invited to take part in a short debrief interview with the Chief Investigator, to provide an understanding of the types of error observed and their causes. There will be a particular focus on how errors relate to the information provided in the monograph. The critical incident technique will be used to investigate whether or not the error was related to the IMG monograph. This approach has been used before to understand the causes of medication errors by exploring the intentions, behaviours and actions of participants involved in a specific situation. Participants will be asked to describe the chain of events leading up to the error, the circumstances in which it occurred, the perceived reasons for the error, and how it might have been prevented.

An interview schedule covering these subjects has been prepared by the Chief Investigator, based on previous relevant research and topic guides . This interview schedule may evolve as data collection progresses, to ensure it adequately reflects issues raised during preceding interviews. Each interview will be audio recorded using a password protected digital recorder, and the interviewer will make field notes. To ensure confidentiality and patient safety, participants will only be invited to take part in an interview when a suitable private room is available and the participant does not have an urgent clinical task to carry out. As soon as practical, the recordings will be transferred to the University of Bath's secure research data storage facility and deleted from the digital recorder. Subsequently, the interview recordings will be transcribed by experienced transcribers employed by the University of Bath. The Chief Investigator will remove any information that could potentially be used to identify a research participant from the transcripts before subsequent analysis and reporting.

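### The single block size of 10 is disclosed to the Chief Investigator, who enrols and observes every nurse; if his debriefs reveal past allocations, later ones in the block become partly guessable

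*Protocol*

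**What the plan says.** The trial is a "randomised parallel group *in situ* simulation experiment with a 1:1 allocation ratio" (section 1.5). Section 3.1 adds "Allocation will be stratified by research site and nursing experience", with experience split at five years, and then "A block size of 10 will be employed". Each block therefore holds five allocations to each group, and no other block size is used.

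Several roles fall to one person:

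- **Recruitment (2.8):** the Chief Investigator visits the ward once the nurse in charge confirms that it is safe. "He will then invite staff to participate in a data collection session and agree a safe time (that day) for this to happen".
- **Assignment (3.3):** "The Chief Investigator will enrol participants and randomly assign them to one of the study groups". The list itself is generated and uploaded by an independent person.
- **Observation (4.1):** he watches each simulation and notes errors on a structured schedule.
- **Debrief (4.1):** he interviews nurses who made an IMG-related error. "There will be a particular focus on how errors relate to the information provided in the monograph".

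Section 3.4 sets out the safeguards. Files are named by randomisation code, a privacy filter covers the laptop screen, nurses are asked not to reveal their monograph, and the link from code to group is withheld until data collection ends. Under Severity determination in 4.1, a seven-member panel scores severity, not the Chief Investigator.

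**The concern.** In a permuted block of known, constant size, each past allocation that becomes known shifts the odds for the next one and can fix the last ones. The safeguards in section 3.4 protect the session in progress. They do not stop someone from reasoning forward from sessions already finished.

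The debrief is where finished sessions can become known. It covers the chain of events, the reasons for the error and how it might have been prevented, all with reference to the monograph used. By then the nurse has also been shown both versions. Section 2.6 puts all procedures on one day, so a debrief normally comes before the next nurse in that stratum is randomised. Amendment 2 in Appendix 2 speaks of a high prevalence of errors, so many nurses could qualify for one.

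A debrief cannot affect how that nurse's own session was recorded, because it comes afterwards. What a known block size adds is a way to carry the information to nurses not yet invited or observed. That could influence whom he invites next, and how he records borderline deviations in error types that need judgement, such as incorrect technique. The panel scores only the errors that he recorded, and about 10% of main-study sessions are videoed for a second observer.

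**Working it through.** **The plan's own figures.** The protocol gives no figure for predictability. Its sample size reproduces and is not affected by this point. With 30% against 15%, two-sided 5% and 80% power, n = [1.960·√(2·0.225·0.775) + 0.842·√(0.30·0.70 + 0.15·0.85)]² / 0.15² = 120.5, so 121 per group.

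**Blocks per stratum.** Section 2.7 says "it is anticipated that four hospitals is the most likely number of study sites". Four sites by two experience levels give 8 strata. The total is 242 (2 × 121) to 344 (2 × 172), which is 242/8 = 30 to 344/8 = 43 nurses per stratum, or about 3 to 4 blocks of 10.

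**Worst case, exact.** With 2m = 10, block size known and every earlier allocation known:

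- Correct guesses = [m + 2^(2m−1)/C(2m,m) − 1/2]/2m = [5 + 512/252 − 0.5]/10 = 6.53/10 = 65.3%.
- Certain allocations = [2m/(m+1)]/2m = (10/6)/10 = 16.7%.
- By position, certainty is 17% for the 8th allocation, 44% for the 9th and 100% for the 10th.

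**Partial knowledge, simulated.** Each earlier allocation in the block is known with probability k, and the guess is the arm less often seen in that block. For the hidden mix, the guesser cannot tell where a block ends and so names the arm that is behind among all revealed allocations in the stratum (40 nurses).

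| k | Fixed 10, correct | Fixed 10, certain | Hidden 10/12/14, correct |
|---|---|---|---|
| 0% | 50% | 0% | 50% |
| 22.5% | 54% | 0% | 52% |
| 50% | 57% | 0.5% | 54% |
| 80% | 61% | 5.5% | 57% |
| 100% | 65% | 16.7% | 63% |

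The documents give no value for k. The 22.5% is only the mean of the planning rates, (30% + 15%)/2, and is a marker on the scale. It is neither an estimate nor a lower bound.

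**Why small blocks should be left out.** Small blocks are easier to guess. A hidden mix of 4, 6, 8 and 10 gives about 66 to 67% correct at k = 100%, slightly worse than the fixed block of 10.

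**The case against.** A reader might infer that printing the block size makes late allocations predictable in itself. The protocol does not support that. Without knowledge of past allocations every guess is 50% at every position, and section 3.4 is designed to keep that knowledge from the Chief Investigator. This objection stands, and it makes the point conditional.

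The debrief is also a narrower route than it first looks. It needs an observed IMG-related error, a free private room, no urgent clinical task and the nurse's agreement. The same amendment that mentions many errors also mentions difficulty finding private space. A nurse may discuss an error without revealing the version: section 2.3 says that both monographs carry the same content, and the preference scale uses neutral labels (guide X and guide Y). So k could be well below the share of nurses with errors.

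Two further inferences go too far. The Chief Investigator does not control recruitment alone, since ward managers agree the times and the nurse in charge confirms safety. Nor does he grade the errors: the panel's mean score sets the moderate-severe threshold, and several error types have numeric limits (5% or 10%). His discretion lies in whether a deviation is recorded.

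Finally, blocks of 10 within strata are a legitimate choice, and varying them does not close the route by which allocations leak. That is correct, and it limits the gain. What remains is that no safeguard in the protocol covers deduction from a known block size once past allocations leak.

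**Conclusion.** The point holds as a minor, conditional weakness. It rests on two assumptions: that the Chief Investigator knows the block size, a safe inference because he runs the trial under this protocol, and that debriefs reveal some past allocations within a stratum.

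On those assumptions the guess rate rises from 50% to between 54% and 65% as k goes from 22.5% to 100%. Certainty matters only at high k: about 0.5% of allocations at k = 50%, 5.5% at 80% and 16.7% at 100%. Nothing in the protocol shows that prediction occurred or that any rating was affected, and no bias in the primary outcome can be calculated from it.

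Hidden varying blocks lower the guess rate by about 2 to 4 percentage points over the non-zero values of k. They also remove the certainty at the block end, provided the set of sizes stays hidden too. The hidden-mix figures assume a simple guesser. A cleverer one might do slightly better, so the gain should be read as approximate.

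**What to change.** In section 3.1, replace "A block size of 10 will be employed" with wording such as: randomly permuted blocks of varying size within each stratum, with sizes chosen by the independent person and not disclosed to the Chief Investigator until data collection ends. Leave out small blocks; 10, 12 and 14 would serve. Keep the sizes in a separate document rather than in the protocol, because printing the set would give back part of what hiding them gains. Apply the change to strata not yet opened.

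The cost is one protocol sentence, the amendment that carries it, and a regenerated list from the person who already makes it. The statistical cost is a slightly larger possible imbalance where a stratum stops mid-block: at most 7 nurses with a block of 14, against 5 with a block of 10. The sample size does not change.

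The leak itself would be reduced by having someone else run the debriefs, or by holding them after recruitment closes at that site. This costs more. It needs a second interviewer, or a later return to nurses for whom section 5.4 keeps no identifying link. If it is not feasible, record which sessions were debriefed before the next allocation in the same stratum, so that the exposure can be reported.

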## 3.2 Allocation concealment

Allocation will be concealed by use of an online randomisation service (www.sealedenvelope.com).

## 3.3 Implementation

The allocation sequence will be generated and uploaded to the online randomisation service by a person independent from the research team. The Chief Investigator will enrol participants and randomly assign them to one of the study groups.

## 3.4 Blinding

The Chief Investigator (responsible for allocation, data collection and analysis) will be blinded to the assignment of interventions. The online randomisation service will produce a unique randomisation code for each participant. The independent person who generates the allocation sequence will create a folder on the data collection laptop computer containing a copy of the appropriate monograph for each

randomisation code. The filenames of these monographs will be the randomisation code to which they are linked.

Once the online randomisation service has allocated a participant to a group, a privacy filter will be placed over the screen of the data collection laptop, which only permits a person looking directly at the screen to see it. This will prevent the observer (Chief Investigator) from learning which monograph is in use, and so he will be blinded during data collection. The participant will be asked to open the monograph file named with their randomisation code on the data collection laptop and to use this during the simulation. Before the file is opened, the Chief Investigator will double check the correct file has been selected.

Once data collection is complete, the independent person will reveal which randomisation codes were allocated to groups A and B, but not which monograph is associated with each group. Data will then be analysed for group A versus group B, and the type of monograph associated with each group will only be revealed once this is complete. In this way, the Chief Investigator will remain blinded during data analysis.

Participants will be required to read their allocated IMG monograph, so cannot be blinded to the intervention. However, they will be unaware of the content of the alternative IMG monograph until the last stage of data collection (completion of the preference score). They will also be asked to avoid revealing any information about their allocated IMG monograph to the investigator.

## 4 METHODS: DATA COLLECTION, MANAGEMENT AND ANALYSIS

## 4.1 Data collection methods

#### Observational data

All data will be collected from each participant during a single individual session. Each session will be arranged to take place whilst the participant is actively working as a nurse in a clinical area at their usual hospital. Each data collection session will take place in the room in the relevant clinical area that is normally used for the preparation of intravenous medicines.

Initially, each participant will provide limited demographic and nursing experience data on a paper data collection form. Some of this information will then be used to confirm eligibility and complete the online stratified randomisation process described in Section 3.

The participant will be given a printed simulated inpatient medication order and administration record for bathicillin, in the format used by their hospital. He or she will also be provided with a vial of placebo powder for reconstitution labelled as "Bathicillin 200mg", as well as a number of other vials of placebo powder for reconstitution labelled as other simulated medicines (such as "bathymicin") or other strengths of bathicillin. These other simulated medicines will make it possible for participants to select the wrong ampoule to make the dose, as can happen in routine practice. The participant will be asked to take any other equipment they require (such as syringes, needles, infusion fluid) from the supplies available for the preparation and administration of intravenous medicines in their clinical area.

As described in Section 3, the participant will then open their allocated IMG monograph on the data collection laptop and will be asked to prepare and administer a dose of bathicillin in accordance with

the simulated medication order, their allocated version of the IMG monograph and all relevant policies or procedures used within their hospital. They will be asked to do this exactly as they would for an actual patient. The dose will be administered to a training manikin arm located in the room in which the dose was prepared.

During these procedures, participants will be unobtrusively observed by the Chief Investigator and any preparation or administration errors noted using a structured, printed observation schedule based on best practice guidelines. Structured observation is the gold standard method in research into medication administration errors.

In addition, the time taken to prepare and administer the dose will be recorded on the observation schedule. The observer will start a stopwatch at the point at which the participant opens their allocated IMG monograph, and stop it when they inform the observer that they would leave the simulated patient's bedside with the infusion running. At this time, the participant will be asked to close their allocated IMG monograph file, so that blinding is maintained.

## Participant feedback measures

Once the preparation and administration of bathicillin is complete, participants will complete a modified Provider Decision Process Assessment Instrument (mPDPAI) questionnaire on the data collection form. This is the only validated tool for measuring health professionals' degree knowledge and uncertainty whilst making decisions. The original PDPAI was designed to measure physicians' degree of comfort with a clinical decision. It comprised of a 12-item questionnaire assessing four different dimensions: uncertainty, knowledge, value and effectiveness. Each question was answered with a 5-point Likert scale and a Decisional Conflict Score (DCS) was calculated by summing the response. A high DCS indicated a greater degree of uncertainty about the decision. Subsequently, the PDPAI has been utilised by a variety of studies, in both its original format and following modifications to its wording, number of items, response scale and language

The psychometric properties of the original PDPAI were initially established in a group of primary and secondary care physicians. Reliability was investigated by quantifying the degree of internal consistency using Cronbach's alpha, giving a result of 0.878. Face validity was assessed using feedback from participants and construct validity was explored by hypothesising that there would be a negative correlation between the DCS and participants' rating of the quality of the decision and their satisfaction with it. Spearman's rank correlation coefficients were -0.58 and -0.52, respectively. Subsequent studies the original or modified versions of the PDPAI also measured internal consistency, resulting in Cronbach's alpha values ranging from 0.78 to 0.82, indicating an acceptable degree of reliability.

The PDPAI has been modified for use in this current study, by removing questions 6, 8, 9 and 10 from the original instrument, as these related to concepts not relevant in this context (risk vs benefit, patient compliance and patient views/understanding). The remaining questions were reworded, to change their focus from a single decision relating to which treatment to choose, to a series of decisions relating to how to prepare and administer bathicillin. In order to investigate the psychometric properties of this modified PDPAI with the participants of this study, the previously used quality and satisfaction validation questions were similarly reworded for use in this study.

Finally, each participant will be shown both versions of the IMG monograph. They will be asked to look at both of them and record which they prefer, using a seven-point rating scale on the data collection form. This approach has been used in previous randomised trials comparing documents used in the generation of clinical guidelines..

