#### 2.2.2 Exclusion criteria

• Participated in phase 1 (user testing) of this study

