#### 2.7 Sample size

There is one published study that reports the rate of moderate to severe errors in the preparation and administration of intravenous medicines to adults on UK hospital wards and which used the same error observation and severity determination techniques as this study. This study observed one or more moderate-severe errors in 30% of 430 intravenous doses. If the definitions to be used for the current study had been applied in this previous research, 27.2% of 430 intravenous doses would have involved one or more moderate-severe IMG-related errors.

Using the same techniques, a larger and more recent, but as yet unpublished study, observed one or more moderate-severe preparation errors in 28% of 1148 adult injectable medicine doses administered on UK hospital wards. This study did not investigate administration errors, but their inclusion would have increased this error rate.

These error rates are supported by other studies, which either took place in other countries or used different severity determination methods, which report similar rates of moderate-severe preparation and administration errors (22-34% of doses).

Therefore, it is reasonable to assume that participants in the "original monograph" group will make at least one moderate-severe IMG-related error in 30% of doses.

Following discussion with the Study Advisory Group, it was agreed that at least one moderate-severe error occurring in 15% of doses would represent a clinically relevant reduction. This is in line with the assumptions underlying other recent research considering the effect of educational interventions on the rate of injectable medicine preparation and administration errors.

Standard calculations indicate that a sample size of 121 participants per group will give an 80% probability of detecting this reduction in the moderate-severe error rate at the 5% significance level, assuming equal group size. This assumes that there is no clustering of the data by hospital site, as NHS hospitals are required to provide similar training for staff preparing and administering intravenous medicines, and to follow similar procedures.

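### Nurses already tested return to wards where colleagues may still be recruited, and the protocol does not ask them to keep the task or the monographs from those colleagues

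*Protocol*

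**What the plan says.** Sections 1.5 and 4.1 give every participant one task: prepare and give a dose of the same invented medicine from a simulated order. In section 4.1 (Participant feedback measures), after the simulation and the decision questionnaire, "Finally, each participant will be shown both versions of the IMG monograph". Those seen to make an IMG-related error may also be invited to a debrief about its causes and prevention, if a private room is free and no urgent clinical task is waiting.

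Sections 2.8 and 4.1 describe recruitment by ward visit. Staff are invited on the ward, a session is agreed for that day, and it takes place while the nurse is on duty in the usual clinical area.

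The protocol treats prior knowledge as a threat in several places:

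- Section 1.5: "As cross-over design will not be utilised, as this would create a serious order effect".
- Section 2.3 renames the medicine so that existing knowledge of it cannot be used.
- Section 2.2.2 has one exclusion: "Participated in phase 1 (user testing) of this study".
- Section 3.4 says of participants that "they will be unaware of the content of the alternative IMG monograph until the last stage of data collection".

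The only request for silence is also in section 3.4: "They will also be asked to avoid revealing any information about their allocated IMG monograph to the investigator".

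**The concern.** The request in section 3.4 protects the observer's blinding. It does nothing for the next nurse on the ward. A participant who has done the task and seen both monographs can go back to colleagues who have not yet been tested and tell them about the displacement-value pitfall, the technique requirements or the differences between the two documents. The protocol has no step to discourage this and none to detect it.

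Two things are at stake. First, the statement that participants do not know the alternative monograph until the end describes what the study itself shows them, and nothing secures it against word of mouth. Second, forewarned nurses would probably make fewer IMG-related errors whichever monograph they use. The group with more errors to lose would lose more, so the absolute difference would shrink. A null result would then be harder to interpret, and because exposure is not recorded, the question could not be examined afterwards.

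**Working it through.** **Inputs from section 2.7.** In the original-monograph group, participants "will make at least one moderate-severe IMG-related error in 30% of doses". For the target, "at least one moderate-severe error occurring in 15% of doses would represent a clinically relevant reduction". On size, "Standard calculations indicate that a sample size of 121 participants per group will give an 80% probability of detecting this reduction", at the 5% level with equal groups. Sidedness is not stated, so two-sided is assumed. The upper size is 172 per group.

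**Reproducing the plan's figure.** With p1 = 0.30, p2 = 0.15 and mean p = 0.225:

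n = [1.96 × √(2 × 0.225 × 0.775) + 0.8416 × √(0.30 × 0.70 + 0.15 × 0.85)]² / 0.15² = 120.5, so 121 per group.

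The plan's figure reproduces. Power is 80.2% at 121 and 91.8% at 172. The second value ignores clustering. The plan's own reason for 172 is a design effect of 1 + 42 × 0.01 = 1.42, and 121 × 1.42 = 171.8.

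**Power formula.** Power = Φ{[(p1 − p2)√n − 1.96√(2p(1 − p))] / √(p1(1 − p1) + p2(1 − p2))}, where p is the mean of p1 and p2.

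**Assumptions not in the documents.** Let c be the share of nurses forewarned. No value of c is given, so 10%, 20% and 30% are shown.

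*Case A: forewarning halves the risk in both arms.* Each rate is multiplied by (1 − 0.5c).

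| c | Original | User tested | Difference (points) | Power, 121 | Power, 172 |
|---|---|---|---|---|---|
| 0 | 30.0% | 15.0% | 15.0 | 80% | 92% |
| 10% | 28.5% | 14.25% | 14.25 | 77% | 90% |
| 20% | 27.0% | 13.5% | 13.5 | 75% | 88% |
| 30% | 25.5% | 12.75% | 12.75 | 72% | 86% |

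The ratio of the two rates stays at 2 throughout. Only the absolute difference and the power fall. If forewarning cuts risk by a quarter instead of a half, power at 121 is 79%, 77% and 76%.

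*Case B: only the original-monograph group gains.* Its forewarned nurses fall to w, with w = 15% or 20%, and the user-tested group stays at 15%. The original rate is 0.30(1 − c) + wc.

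| c | Original (w = 15% / 20%) | Difference (points) | Power, 121 | Power, 172 |
|---|---|---|---|---|
| 10% | 28.5% / 29.0% | 13.5 / 14.0 | 72% / 75% | 86% / 88% |
| 20% | 27.0% / 28.0% | 12.0 / 13.0 | 63% / 69% | 78% / 84% |
| 30% | 25.5% / 27.0% | 10.5 / 12.0 | 53% / 63% | 68% / 78% |

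Case B is the harsher case. With w = 15%, it supposes that hearsay works as well as the user-tested monograph and that nurses already using that monograph gain nothing from it.

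**The case against.** The strongest reply is that nothing shows leakage happens. The protocol does not say how many nurses are tested per ward or how visits are spaced, and second-hand talk is weaker than doing the task. That stands: this is a risk of unknown size.

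A reader might infer that the order effect for which section 1.5 rejects a cross-over has come back in. The documents do not support that. In a cross-over the same nurse repeats the task after first-hand practice. Here any knowledge would come from someone else, so there is no internal contradiction.

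A reader might also infer bias in favour of one monograph. Allocation is concealed, 1:1, and stratified by site and experience, so exposure should fall on both arms about equally. For a superiority comparison the expected direction is towards no difference, not towards a false benefit.

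Three further points stand. Picking a vial of a different look-alike medicine is coded as a non-IMG-related error, so advance warning of that trap largely bypasses the primary outcome. The debrief is conditional, and the protocol does not say that correct answers are given in it. The participant information sheet is not shown and may already ask for silence.

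These points limit the concern without removing it. The protocol spells out the request towards the investigator and has no counterpart towards colleagues. Nor does it describe any record of prior exposure, which cannot be recovered once data collection is over.

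**Conclusion.** The concern holds as a conduct gap with a cheap remedy. Each step of the route is in the protocol, and it states no safeguard against it. The likely consequence is some dilution of the difference and some loss of power, with neither arm favoured. On the more even assumption (10-30% forewarned, risk halved in both arms), the loss is about 3 to 9 percentage points of power at the minimum size, and power stays at 86% or above at 172 per group before any allowance for clustering. Power as low as 53% arises only if 30% are forewarned, the gain is confined to the original-monograph group, and those nurses reach the user-tested rate. That figure should not be read as an estimate. All these values rest on assumed shares and effects. The documents give neither.

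**What to change.** - **Sections 4.1 and 5.3.** At consent and again at the end of the session, ask each participant not to discuss the task, either monograph or the errors with colleagues until data collection at that hospital is finished. If the participant information sheet already asks this, refer to it in the protocol.
- **Existing paper form, before randomisation.** Record whether the nurse has heard details of the task from a colleague, together with ward and order within ward.
- **Section 4.3.** Keep every participant in the primary analysis as randomised, and add one sensitivity analysis omitting nurses who report prior exposure.
- **Section 2.2.2 (optional).** State that nobody takes part twice, pilot rounds included. Section 4.1 already collects all of a participant's data in a single session, so this only clarifies.

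The cost is a few sentences in the consent process and session script, a few form fields and one extra analysis. The request cannot be enforced, exposure is self-reported, and the sensitivity analysis will have slightly fewer participants.
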